10.3.4.1 Wound healing

The investigator will assess the surgical wound and indicate if it is "completely healed" [No/Yes]. Completely healed is to be judged as a problem-free skin around the abutment. Skin dehiscence does not necessarily contradict complete healing.

10.3.4.2 Holgers score

Classification of skin reactions around skin penetrating implants will be made using the Holgers score [16]. The Holgers classification is a scale from 0 to 4 that is used to grade skin reactions. Grade 0 indicates a reaction-free area whereas 4 indicates a severe infection often requiring removal of the implant.

Holgers score	
0	No reaction
1	Erythema with slight swelling around abutment
2	Erythema, moistness and moderate swelling
3	Erythema, moistness and moderate swelling with granulation around abutment
4	Overt signs of infection resulting in removal of implant

10.3.4.3 IPS-scale

The IPS scale [17] is a new, consistent and uniform assessment scale for both percutaneous and transcutaneous implants for bone conduction devices. For percutaneous implants, the IPS-scale is comprising three parts: inflammation, pain, and skin height, with higher scores reflecting more severe complication. It assesses the following characteristics:

1. Inflammation:
 - Skin Integrity (intact = 0/ not intact = 1)
 - Not intact = observation of a blood crust or persistent minimal blood loss at the skin-abutment junction.
 - Erythema (none = 0/ present = 1)
 - Edema (none = 0/ present = 1)
 - Granulation tissue formation (none = 0/ present = 1)
2. Pain:
 - None = 0
 - Present, but no increase during manipulation abutment AND <6 wks present = 1
 - Present, and increase during manipulation abutment AND/OR >6 wks present = 2

CONFIDENTIAL

- Manipulation = tightening (if needed) or tapping on the abutment
- 3. Skin height:
 - Normal = 0
 - Increased, but able to couple sound processor = 1
 - Above rim abutment/unable to couple sound processor =2

The ratings result in a score compiling the ratings of each parameter, i.e. $I_xP_xS_x$.

The IPS-scale offers a standardized treatment advice for each IPS-scale:

- $I_{0-1}P_0S_{0-1}$ = no treatment
- $I_0P_1S_{0-1}$ = no treatment
- $I_1P_1S_{0-1}$ = local topical treatment
- $I_{2-3}P_{0-1}S_{0-1}$ = local topical treatment
- $I_{0-4}P_2S_{0-1}$ = consider addition of systemic treatment for possible peri-implantitis
- $I_{0-4}P_{0-2}S_2/ I_4P_{0-1}S_0$ = consider revision/removal surgery or longer abutment (in combination with antibiotic treatment, depending on I and P-score)

It is not mandatory to follow the treatment advice, but upon analysis of the data from the study, the actual treatment given to the patients will be compared to the treatment advice as a means of evaluating the scale.

10.3.4.4 Skin overgrowth

A thickening of the skin/soft tissue surrounding the implant/abutment complex can cause problems when attaching the sound processor and may also increase the risk of feedback problem. Clinically significant skin/soft tissue overgrowth is assessed by the investigator to determine if skin overgrowth prevents the use of the sound processor [No/Yes].

10.3.5 Post-operative events

Post-operative complications at implant site are assessed at all post-operative visits, with emphasis on:

- Bleeding and/or hematoma
- Hair in-growth
- Skin dehiscence around the abutment

Note: If the event is judged as untoward (exceeding what is normally expected according to surgeon's judgement) it should be reported as an adverse event.

10.3.6 Pain assessment

The patient is asked if pain around the abutment is present [No/Yes].

If pain is present [=Yes]:

- Magnitude will be recorded using an NRS [scale from 0 = no pain to 10 = worst imaginable pain].
- Subject will also be asked if perceived level of pain prevents use of the sound processor [No/Yes], if applicable.
- Subject will be asked if pain increases with manipulation of the abutment [No/Yes]

If pain is not present [=No]:

- NRS score of 0, [0 = no pain] will be implicit.

CONFIDENTIAL

oticon MEDICAL	Title BC108 CIP MONO	Document no Doc-00068506	Revision 2	Page 33(48)
--------------------------	--------------------------------	------------------------------------	----------------------	-----------------------

10.3.7 Numbness assessment

The patient is asked if numbness around the abutment is present [No/Yes]. If numbness is present [=Yes], the patient is asked to judge the numbness magnitude using an NRS [scale from 0 = no numbness to 10 = complete numbness] and the circular area of numbness will be recorded as the diameter in cm of the circle, with the abutment at the centre.

10.3.8 Sound processor usage

The subject will be asked for the average number of hours per day and days per week of sound processor usage since their last visit. The question will only be asked at study visits that occur after sound processor fitting.

10.3.9 Patient Reported Outcome (PRO)

10.3.9.1 Glasgow Benefit Inventory (GBI)

The Glasgow Benefit Inventory (GBI) is a general health-related quality of life measure, developed for otorhinolaryngologic conditions. The GBI uses a scale from -100 to +100, where scores above 0 indicate improved quality of life [18]. In addition to the total GBI score, subscales for general, social and physical will be analysed. The GBI-questionnaire is to be filled in by the patient three months after surgery.

10.3.10 Concomitant treatment and medication

Medication which is considered necessary for the patient's safety and well-being may be given at the discretion of the investigator. The administration of this medication and all medication for adverse events must be recorded in the appropriate section of the eCRF.

10.4 Safety assessment

Subjects will be observed and asked about 'any health problems since last visit' during all visits in the investigation. Information that will be collected includes:

- Event description
- Start and stop dates
- Action taken due to the event
- Clinical outcome of event
- Serious: no/yes (if 'yes' more information is required)
- Device/procedure related: no/yes (if 'yes' more information is required)

All occurring adverse events will be registered, tabulated and accounted for in a safety data listing. The safety endpoint will consist of a descriptive summary, including frequency, causality, severity and duration of related events at three and 12 months after surgery. See section 19 for further reference.

11 MONITORING

During the investigation, representatives from Oticon Medical will have regular contacts with the investigational sites with the purpose to oversee the investigation. Monitoring activities will be performed by appointed monitors according to applicable standards (i.e. ISO14155) and internal guidance documents. The overall purposes of the monitoring are to make sure that the rights, safety and welfare of the research subjects are protected, that the reported data are accurate, complete, and verifiable from source documents, and the conduct of the clinical investigation complies with

CONFIDENTIAL

the approved CIP, subsequent amendments (if any), applicable standards (i.e. ISO14155), and applicable regulatory and ethics committee requirements.

11.1 Monitoring Plan

It is estimated that there will be around three physical on-site monitoring visits at each site during the duration of the investigation: a site initiation visit (may be held remotely if training in the surgical technique has already been performed), an interim monitoring visit and a close-out visit. Should the need for an increase of on-site monitoring visits occur, e.g. for quality concerns, this will be decided on a case by case basis.

For the first two enrolled subjects at each site, 100% source data verification (i.e. comparison of data entered into the eCRF against source data) will be performed, and thereafter for every fourth enrolled subject (i.e. 25%). This level may be increased if deemed necessary. Queries will be raised within the Electronic Data Capture (EDC)-system for any discrepancies found during the monitoring activities.

The Investigator Site File (ISF) will be reviewed for accuracy and completeness throughout the investigation.

As a complement to the physical monitoring visits, centralized or remote (i.e. off-site) monitoring will be performed on an interim basis by e.g. reviewing the data entered into the EDC-system.

Further details on the extent and nature of monitoring activities as well as access to source data, and the strategy of source data verification will be outlined in a study specific, risk-based, Monitoring Plan.

11.2 Audits and inspections

Audits of the clinical investigation may be conducted by authorized sponsor representatives or third parties designated by the sponsor to evaluate compliance with the CIP, agreements, ISO 14155, and the applicable regulatory requirements. These audits may cover all involved parties, systems and facilities and are independent of, and separate from, routine monitoring or quality control functions. The institution's quality assurance department (or equivalent) may also visit the investigation site to perform an audit.

12 STATISTICAL DESIGN AND ANALYSIS

12.1 Study design and analysis populations

The investigation is a multinational, multicentre, prospective, single-arm investigation to establish the level of successful implant/abutment complex installations using the MONO surgical procedure. Fifty patients will be included to prospectively study the proportion of implant/abutment complexes that are performing as intended (thus capable of providing a reliable anchorage for the sound processor) three months after using the MONO surgical procedure.

Three analysis populations will be defined in the investigation, i.e. safety-, intention-to-treat- (ITT) and per-protocol- (PP) analysis populations. The data used for the safety-population analysis will include relevant safety data from all consenting subjects in the study. The ITT population will include all subjects undergoing surgery in the investigation. The PP population will include treated subjects that do not have any significant protocol deviation.

12.2 Sample size

The sample size in the investigation is not hypothesis-driven, but rather based on:

1. The typical size of prospective studies on surgical outcomes within the bone-anchored hearing system field.
2. The precision of the primary endpoint. The precision can be expressed as the width of the two-sided 95% confidence interval (CI).

Prospective studies from recent years were identified through literature search as part of the clinical evaluation. One study was excluded (Dumon *et al.* 2016) since it covered a period of 12 years, which cannot be considered as typical. The identified studies (Table 6) included a median of 25 patients and an average of 35 patients. For larger comparative studies the group size varied from 21 to 39 patients.

Table 6. Prospective BAHS-studies published between July 2016 and June 2019

Year	Title	Author	Implant Test (N)	Implant Control (N)	Adult (N)
2018	Minimally Invasive Ponto Surgery Versus the Linear Incision Technique With Soft Tissue Preservation for Bone Conduction Hearing Implants: A Multicenter Randomized Controlled Trial.	Calon et al.	33	30	63
2019	Three-Year Clinical and Audiological Outcomes of Percutaneous Implants for Bone Conduction Devices: Comparison Between Tissue Preservation Technique and Tissue Reduction Technique.	Kruyt et al.	25		25
2017	Bone Anchored Hearing Implant Surgery: 1 Year Follow-Up Data Shows No Effect of Hydroxyapatite Coating on Soft Tissue Reaction after Loading at 1 Week.	Høgsbro et al.	25		25
2018	Three-year Outcomes of a Randomized Controlled Trial Comparing a 4.5-mm-Wide to a 3.75-mm-Wide Titanium Implant for Bone Conduction Hearing.	Kruyt et al.	39	21	57
2018	The clinical outcome and microbiological profile of bone-anchored hearing systems (BAHS) with different abutment topographies: a prospective pilot study.	Trobos et al.	5	7	12
2018	Wide diameter bone-anchored hearing system implants: a comparison of long-term follow-up data between tissue reduction and tissue preservation techniques.	Reznitsky et al.	24	24	48
2017	Baha implant as a hearing solution for single-sided deafness after retrosigmoid approach for the vestibular schwannoma: surgical results.	Boucek et al.	5	11	16

The primary endpoint of this investigation is the ‘capability of implant/abutment complex to provide a reliable anchorage for the sound processor at three months after MONO surgical procedure’. The primary endpoint will be presented by a point estimate (of the proportion) combined with a two-sided 95% CI, to reflect the level of successful implant/abutment complex installations using the MONO surgical procedure. Assuming a ‘success rate’ of 85% (conservative approach) three months after surgery, and with a confidence interval width of 20% points, the sample size needed is 50 patients. With a proportion of loadable implant/abutment complexes at three months of 95%, the resulting CI would be 11%.

Based on the above, the sample size was decided to be 50 patients.

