10.3 Clinical investigation assessments

10.3.1 *Implant/abutment complex capability to provide a reliable anchorage for a sound processor after MONO surgical procedure*

The primary endpoint variable of this study ('capability to provide a reliable anchorage for a sound processor') is a composite variable depending on the outcome of five other variables:

- I. Implant in situ [Implant survival: No/Yes] (see section 10.3.2);
- II. Implant stable [Implant stability: No/Yes] (see section 10.3.3);
- III. Absence of:
 - a. adverse skin reaction (Holgers score ≥ 2) preventing use of sound processor [No/Yes] (see section 10.3.4.2);
 - b. pain preventing use of sound processor on implant/abutment complex [No/Yes] (see section 10.3.6);
 - c. skin overgrowth preventing use of sound processor on the implant/abutment complex [No/Yes] (see section 10.3.4.3)

For this composite endpoint to result in a positive outcome [=Yes], all involved variables need to be answered with [Yes]. If any involved variable is answered with [No], the outcome of the composite variable will be considered a failure [=No]. The rate of subjects (or implant/abutments complexes, if a subject is treated bilaterally) with a positive outcome will be used to calculate point estimates of the proportions with a two-sided 95% confidence interval. These point estimates and corresponding confidence intervals will be used to establish the expected level of implant/abutment complexes that are capable to provide a reliable anchorage (i.e. usage) for a sound processor, at the respective time point.

10.3.2 *Implant survival*

At each follow-up visit, the Investigator will assess whether the implant is still in situ (in place) by means of a [No/Yes] question. The rate of implant survival will be calculated from the number of

implants in situ over the number of implants that were placed. The rate of implant failure will be implicit. The reason for any failure (e.g. spontaneous, trauma etc.) will be documented.

10.3.3 *Implant stability*

Implant stability will be assessed by means of the subjective clinical judgement of the investigator. If the implant is firmly situated in the bone and assumed to be sufficiently osseointegrated when gently manipulating the implant/abutment using the fingers, it is judged stable [Yes]. If the implant is loose, with a lack of osseointegration, the implant is judged not stable [No].

10.3.4 *Skin assessments*

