12.3 Statistical methods and analytical procedures

Descriptive statistics will be used. The primary endpoint will be presented both as number and percentage, and by point estimates of the proportions combined with a two-sided 95% CI.

For secondary endpoints, the distribution of categorical and dichotomous variables will be presented both as number and percentage, although the composite variable will be presented as for the primary endpoint. Data will be presented for each time separately as well as across visits, where applicable. The distribution of continuous variables will be given as Mean, standard deviation (SD), Median, Minimum and Maximum.

For the safety endpoint, device deficiencies, adverse events and serious adverse events related to the device will be descriptively reported using frequency tables and listings.

All statistical analyses are to be explained in detail in a statistical analysis plan (SAP). Any deviations from the original analysis plan will be described in a CIP amendment, as deemed appropriate.

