12.4 Missing data and special considerations

Missing data will not be imputed. For the primary endpoint, subjects withdrawn from the study due to loss of implant placed during the study (extrusion or elective removal) will be included in the analysis as a treatment failure (i.e. implant/abutment complex not in situ).

In case of any bilaterally implanted patient, implants will be handled as independent from each other for all implant-related variables, since this is considered more clinically relevant. Patient-variables such as patient characteristics and questionnaires will be presented on a patient-level.

No bias nor confounding factors are expected due to the single-arm design.

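### The 11-point confidence interval width stated for a 95% success rate with 50 patients is about 2 to 3 points too narrow

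*Combined protocol and SAP*

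**What the plan says.** Section 12.2 says that the sample size is not driven by a hypothesis. It rests on the usual size of studies in the field and on precision, defined as the full width of the two-sided 95% confidence interval for the primary endpoint. Two scenarios follow:

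- At an assumed success rate of 85%, "with a confidence interval width of 20% points, the sample size needed is 50 patients".
- At a higher rate: "With a proportion of loadable implant/abutment complexes at three months of 95%, the resulting CI would be 11" per cent.

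The decision for 50 patients is then drawn from this material as a whole. Section 10.3.1 says that the rate of positive outcomes "will be used to calculate point estimates of the proportions with a two-sided 95% confidence interval". Section 12.3 extends the same presentation to the 6- and 12-month composite ("although the composite variable will be presented as for the primary endpoint"). Neither section names an interval method. Section 12.3 leaves the detail to a statistical analysis plan whose text is not in the supplied document, so the point here is the printed figure and not the absence of a method.

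**The concern.** A proportion of 95% with 50 observations lies close to the boundary at 100%. The simple normal approximation does badly there: its upper limit passes 100%, and it covers the true value less often than it claims. A width of 11 points looked too small for a sound 95% interval.

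The study has no comparator and no test, so the estimate and its interval are the primary result. A reader who takes the 11 points at face value would expect a 95% result to exclude rates below about 89%. If the lower limit is in fact near 85%, such a result only just excludes the plan's own conservative planning rate.

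**Working it through.** **Inputs.** From Section 12.2: n = 50; two-sided 95% level, so z = 1.96; proportions 0.85 and 0.95; precision means full width.

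**Step 1: reproduce the plan's figures (Wald).** The interval is p ± z·√(p(1−p)/n).

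- p = 0.85: √(0.85 × 0.15 / 50) = 0.0505. The interval is 75.1% to 94.9%, width 19.8. This matches the stated 20.
- p = 0.95: √(0.95 × 0.05 / 50) = 0.0308. The interval is 88.96% to 101.04%, width 12.1. Cut at 100%, the width is 100 − 88.96 = 11.04. This matches the stated 11.

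At p = 0.95 the other intervals tried (Wald and Wilson with continuity correction, Wilson, Clopper-Pearson, Agresti-Coull, Jeffreys) do not give 11.

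**Step 2: other intervals at p = 0.95.**

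- Wilson: centre (p + z²/2n)/(1 + z²/n) = (0.95 + 0.0384)/1.0768 = 0.9179. Half-width [z/(1 + z²/n)]·√(p(1−p)/n + z²/4n²) = 0.0665. The interval is 85.1% to 98.4%, width 13.3.
- Clopper-Pearson (beta quantiles, x = 47.5): 84.9% to 99.2%, width 14.3.

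The excess over the plan's 11.0 is 2.3 points (Wilson) or 3.3 points (Clopper-Pearson).

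**Step 3: width and exact coverage at n = 50.** Coverage is the sum of the binomial probabilities of those counts 0 to 50 whose interval contains the true rate.

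| Method | Width at 85% | Coverage at 85% | Width at 95% | Coverage at 95% |
|---|---|---|---|---|
| Wald | 19.8 | 94.1% | 12.1 (11.0 cut) | 92.0% |
| Wilson | 19.7 | 95.6% | 13.3 | 96.2% |
| Clopper-Pearson | 21.45 | 97.3% | 14.3 | 98.8% |

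**Step 4: whole counts.** 95% of 50 is 47.5, which cannot be observed.

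- 47/50: Wilson 83.8% to 97.9% (14.2); Clopper-Pearson 83.5% to 98.8% (15.3).
- 48/50: Wilson 86.5% to 98.9% (12.4); Clopper-Pearson 86.3% to 99.5% (13.2).

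Averaged over all outcomes at a true rate of 95%, the expected width is 12.9 (Wilson) or 13.8 (Clopper-Pearson). All of these exceed 11.

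**Step 5: fewer evaluable results.** Section 12.4 says "Missing data will not be imputed", and Section 9.4.4 does not replace patients who withdraw after implantation. If 45 of 50 were evaluable (an assumed 10% loss), Wilson gives 20.8 points at 85% and 14.1 at 95%.

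**The case against.** The strongest reply is that this is a choice of method and not an error. The 11 reproduces, the plan names no method, and the plan never prints a lower limit of 89%. At the achievable result 48/50 the uncut Wald width is 10.9 and the Jeffreys width 11.4, and both round to 11. The denominator may also exceed 50: bilateral surgery is allowed and "implants will be handled as independent from each other for all implant-related variables". With an illustrative 60 complexes the Wald width at 95% is 11.03; with 70 the Wilson width is 10.99. Finally, Wilson is not faultless near 100%: its coverage is 94.4% at a true rate of 94.5%, 93.7% at 97% and 92.2% at 98%.

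Some of this stands. The 11 is not an arithmetic slip, the 89% is implied and not stated, the exact lower limit depends on the count observed, and Wilson's dips below nominal should be acknowledged.

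The rest does not rescue the figure. A result of 48/50 is 96%, not the 95% that the plan specifies. Jeffreys at 95% gives 12.5 points, with 88.5% coverage at that rate. The sample size calculation is for 50 patients, and the number of bilateral cases is not given. A figure that needs an interval with 92.0% coverage, cut at 100%, does not describe the precision of a 95% interval.

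**Conclusion.** The concern holds, at minor severity. For 50 independent, evaluable complexes and a success rate of 95%, the stated width of 11 points is too small by about 2 points (Wilson) or 3 points (Clopper-Pearson). The lower limit is about 85% by either method, against an implied 89%.

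The planned size does not change. It rests on the 85% scenario, which is correct under Wald (19.8) and Wilson (19.7), and on typical study size. Under Clopper-Pearson the 85% width is 21.45 points, and a 20-point width would need about 58 patients; with that method the target should be restated. No decision rule is affected, because the plan has none. That the plan used a truncated Wald interval is inferred from the match at 11.04.

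**What to change.** In Section 12.2, replace the two width sentences with text such as:

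> For 50 independent, evaluable implant/abutment complexes, the two-sided 95% confidence interval (Wilson score method) is about 20 percentage points wide at a success rate of 85% (72.6% to 92.4%) and about 13 points wide at 95% (85.1% to 98.4%).

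In Section 12.3, add that the intervals for the composite endpoint at 3, 6 and 12 months use the Wilson score method, consistent with the SAP.

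Wilson is suggested because, of the three methods tabulated, its coverage is closest to 95% across the two planning rates together (95.6% and 96.2%). If the sponsor or the SAP prefers Clopper-Pearson, which keeps at least nominal coverage near 100%, state about 21 points (72.1% to 93.5%) and about 14 points (84.9% to 99.2%), and restate the 20-point target. Keep 50 patients in either case.

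The cost is two edits to the text and no extra patients. The stated precision at 95% becomes 2 to 3 points less favourable.
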